	Appendix 2:[†] TELEPHONE FOLLOW-UP QUESTIONNAIRE	35
	Appendix 3: PROTOCOL AMENDMENT HISTORY	41

OZ1: Clinical Protocol OZ1-HV1-202 Amendment 4; 07 June 2017

CONTACT INFORMATION†

SPONSOR

Name Janssen-Cilag Pty Ltd

Address [name]
[name]
Australia

General Contact Number: [REDACTED]

Fax [REDACTED]

Serious Adverse Event Reporting:

Name Janssen-Cilag Pty Ltd Drug Safety Department

Office Phone Number [REDACTED]

SAE Fax Number [REDACTED]

E-mail [REDACTED]

Appropriate Sponsor Contact Personnel:

Name Dr. [REDACTED]

Function Project Physician

Office Fax Number [REDACTED]

Cell Phone Number [REDACTED]

Name [REDACTED]

Function Project Manager

Office Phone Number [REDACTED]

Office Fax Number [REDACTED]

Home Phone Number NA

Cell Phone Number [REDACTED]

Name _____

Function _____

Office Phone Number _____

Office Fax Number _____

Cell Phone Number _____

If any Sponsor contact information needs to be changed during the course of the study, written notification will be provided to the Investigator and will not require (a) Protocol amendment(s).

OZ1: Clinical Protocol OZ1-HV1-202 Amendment 4; 07 June 2017

PROTOCOL VERSION INFORMATION†

Sections of this protocol have been revised. Amendment 1 was issued on 23 June 2006. Amendment 2 was issued on 28 August 2007. Amendment 3 was issued on 15 October 2008. Sections marked “†” have been revised as Amendment 4; 07 June 2017. Please refer to [Appendix 3](#) – Protocol Amendment History for a detailed description of the specific changes.

OZ1: Clinical Protocol OZ1-HV1-202 Amendment 4; 07 June 2017

A long term follow-up protocol to evaluate the safety and survival of autologous CD34+ hematopoietic progenitor cells transduced with an anti-HIV-1 ribozyme (OZ1) in patients with HIV-1 infection

SYNOPSIS

OBJECTIVE†

The objective of this study is to evaluate the long-term safety of a cell-delivered ribozyme gene transfer product (OZ1) in patients infected with HIV-1. OZ1 comprises a Moloney Murine Leukemia Virus based retroviral vector (LNL6) containing a gene that encodes an anti-HIV ribozyme. It is currently a recommendation of the United States Food and Drug Administration (FDA) and Australian Therapeutic Goods Administration (TGA) that all individuals receiving retroviral gene transfer products are followed to collect data on delayed adverse events.

OVERVIEW OF STUDY DESIGN†

This will be a follow-up study of patients previously enrolled in the OTH/OZ1-INT-1 trial. All patients in this protocol will be reviewed at six monthly intervals until year 5 post infusion. Thereafter all patients will be reviewed annually, on the anniversary of the infusion until withdrawal or study completion. Patients who were enrolled in the placebo arm will be discontinued after OTH/OZ1-INT-1 has been unblinded.

STUDY POPULATION

Participants in the OTH/OZ1-INT-1 Phase II study entitled “A Randomized Phase II, double blind, controlled trial to evaluate the safety and efficacy of autologous CD34+ hematopoietic progenitor cells transduced with placebo or an anti-HIV-1 ribozyme (OZ1) in patients with HIV-1 infection” will be asked to consent to continue safety monitoring and gene marking as described in this protocol.

DOSAGE AND ADMINISTRATION

All participants of the OTH/OZ1-INT-1 Phase II study received a single dose of placebo or OZ1 transduced CD34+ cells.

SAFETY EVALUATIONS†

Follow-up will be conducted as per current FDA/Center for Biologics Evaluation and Research (CBER) recommendations. Evaluations will include monitoring for related adverse events such as the development of replication competent retrovirus (RCR), predominant integration sites and insertional oncogenesis. Blood samples will be collected for archival storage for assessment of replication competent retrovirus (RCR) and other safety testing as necessary.

EFFICACY EVALUATIONS

Ongoing analysis of quantitative marking of the gene transfer product (OZ1 and LNL6) in peripheral blood mononuclear cells (PBMC) will be performed as part of the testing of predominant integration sites. These marking data will also be analyzed independently of the integration analysis to detect changes in the number of cells carrying the gene transfer product.

TIME AND EVENTS SCHEDULE

Follow up visits may be part of routine clinic visits where possible, but must be performed as described in the Time and Events Schedule. Additional unscheduled visits will be made if clinical or biological findings, as described in this protocol, require additional evaluation or investigation or as directed by the Investigator.

OZ1: Clinical Protocol OZ1-HV1-202 Amendment 4; 07 June 2017

TIME AND EVENTS SCHEDULE[†]

Follow up visit	Yr 2.5	Yr 3	Yr 3.5	Yr 4	Yr 4.5	Annual Yr 5+ /End-of- Study ⁴
Clinical history and examination	X	X	X	X	X	X
Complete Blood Count/Differential and Platelets	X	X	X	X	X	X
Plasma archive		X		X		X
PBMC archive ¹		X		X		X
OZ1 integration site (PCR) ²	X	X	X	X	X	X
Adverse Events Assessment	X	X	X	X	X	X
Contact details updated for subject and nominated secondary contact	X	X	X	X	X	X
Volume of blood drawn at visit (ml)³	30	73	30	73	30	73

¹The PBMCs will be stored as cryopreserved cells and cell pellets for assessment of replication competent retrovirus (RCR) and other safety testing as required.

²This includes both marking (quantitative OZ1/LNL6 DNA-PCR) and the detection of predominant integration sites. If the percentage of cells marked by the vector (quantitative OZ1/LNL6 DNA-PCR) is less than 1% of the test cell population, the site of integration will not be investigated. If a predominant OZ1 integration site is detected, the patient will be retested within 3 months to determine if it persists. If so, the site of integration of OZ1 will be sequenced and mapped to the human genome to determine any association with a known human oncogene. In all instances that a predominant integration site is present and, particularly when there is expansion of a cellular clone, the patient will be monitored for signs of cancer, so that treatment can be initiated as early as possible. Ongoing analysis of quantitative marking of the gene transfer product will be performed as part of the testing of predominant integration sites. These marking data will also be analyzed independently to detect any changes in the number of cells carrying the gene transfer product.

³Blood can be collected up to 1 week prior to the other assessments.

⁴ End-of-Study assessments will be performed after all ongoing patients have been followed up for least 10 years post-infusion. End-of-Study visits will be completed by 30 November 2017. In the event that a patient cannot attend a site visit, telephonic follow-up will be an acceptable alternative.

OZ1: Clinical Protocol OZ1-HV1-202 Amendment 4; 07 June 2017

INVESTIGATOR AGREEMENT†

OZ1: Clinical Protocol OZ1-HV1-202 Amendment 4; 07 June 2017

INVESTIGATOR AGREEMENT†

I have read this protocol and agree that it contains all necessary details for carrying out this study. I will conduct the study as outlined herein and will complete the study within the time designated.

1. INTRODUCTION

1.1 Background[†]

OZ1 is a Moloney Murine Leukemia Virus based retroviral vector (LNL6) containing a gene that encodes an anti-HIV-1 ribozyme directed against the human immunodeficiency virus type 1 (HIV-1) regulatory gene *tat*.^{13,14,15} A Phase I study demonstrated that the introduction of OZ1 into CD34+ cells *ex vivo* is technically feasible and safe.¹ The international, multi-center, Phase II, randomized, double-blind trial, OTH/OZ1-INT-1, was initiated to investigate the safety and efficacy of OZ1-transduced autologous CD34+ cells in patients with HIV-1 infection.⁹ One patient was enrolled in a Phase II protocol comparing the retroviral vector alone (LNL6) and OZ1. In a protocol amendment, OTH/OZ1-INT-1 became a placebo-controlled trial. Of the 74 patients to be enrolled in the placebo controlled protocol, approximately half received a placebo and half OZ1. The primary efficacy end point is the difference in viral load between the two groups at weeks 47 and 48 post-infusion. Patients continue in the OTH/OZ1-INT-1 treatment interruption follow-on phase until week 100 post-infusion as long as the viral load remains below 100,000 copies/ml, the CD4+ cell count is greater than 150 cells/mm³ and there are no other reasons to recommence antiretroviral therapy. At the end of the OTH/OZ1-INT-1 study (week 100 post-infusion), patients are invited to enter this long term follow-up (LTFU) protocol.

1.2 Rationale for Study[†]

Food and Drug Administration (FDA)/Center for Biologics Evaluation and Research (CBER) recommends a 15-year time-period for follow-up observations. However, CBER also recognizes that assessment of risk is a continuous process, and the nature and duration of follow up observations may be revised accordingly.⁴ This follow up protocol is to assess the long-term safety of OZ1/LNL6 gene transfer product in patients who were enrolled in the OTH/OZ1-INT-1 study. Based on the integrated safety analysis of observations up to 10 years in this LTFU study, up to 15 years with the same OZ1/LNL6 gene transfer product in 2 Phase 1 LTFU studies (OZ1-HV1-101 and OZ1-HV1-102), and published reports of adverse events observed with gene therapeutic products using the same type of retroviral vector,^{2,3,5,6,7,8,10,11,12} the sponsor has determined that the risk to OZ1/LNL6 gene transfer product to recipients beyond 10 years post-infusion is minimal. Accordingly, this long term follow up study will conclude by 30 November 2017. This completion date represents a minimum of 10 years follow up following the receipt of OZ1/LNL6-modified CD34+ cells.

2. OBJECTIVES

1. To undertake long term safety monitoring for any development of:
 - a. Clonal expansion of cells with a predominant OZ1 insertion site
 - b. Insertional oncogenesis
2. To archive/store plasma and PBMC samples for other safety testing that may be required.
3. To assess quantitative marking of the gene transfer product in PBMCs over time.

3. OVERVIEW OF STUDY DESIGN

The patients who were enrolled in the OTH/OZ1-INT-1 trial entitled “A randomized Phase II, double blind, controlled trial to evaluate the safety and efficacy of autologous CD34+ hematopoietic progenitor cells transduced with placebo or an anti-HIV-1 ribozyme (OZ1) in patients with HIV-1 infection” will continue to be assessed under this long term follow-up protocol. Where possible follow up visits will coincide with routine clinic visits.

4. COMPLIANCE[†]

1. The semi-annual visit interval is 6 months \pm 6 weeks (for years 2.5-5). The annual visit interval is 12 months \pm 12 weeks (year 5+) except the End-of-Study visit. End-of-Study assessments will be performed after all ongoing patients have been followed up for least 10 years post-infusion. End-of-Study visits will be completed by 30 November 2017. In the event that a recipient cannot attend a site visit, a telephonic follow-up will be an acceptable alternative.
2. Complete Blood Count/Differential data will be obtained specifically as part of the follow up procedures.
3. In the event that a recipient dies, irrespective of cause of death or time after the gene transfer procedure, a request will be made by the Principal Investigator to the next of kin for an autopsy to assess for the presence of 1) RCR and 2) LNL6 or OZ1 containing cells. If efforts to obtain permission for an autopsy are unsuccessful or not practicable, failure to undertake an autopsy will not be considered protocol non-compliance. If an autopsy is performed, a copy of the autopsy report will be obtained and the cause of death and any significant observations noted in the Serious Adverse Event report.

4. In the event that the recipient undergoes a biopsy or surgical removal of a tumor, an attempt will be made by the Principal Investigator to obtain a sample of tissue for the assessment of the presence of 1) RCR and 2) LNL6 or OZ1 containing cells. If efforts to obtain a tissue sample are unsuccessful or not practicable, it will not be considered as protocol non-compliance.

5. STUDY POPULATION

5.1 Inclusion Criteria

Patients must satisfy the following criteria before entering the study:

- Received the Final Cell Product infusion in the Phase II trial, OTH/OZ1-INT-1.
- Signed Informed Consent Form for this study.

5.2 Exclusion Criteria

All patients who were enrolled in the OTH/OZ1-INT-1 study and received the final cell product will be invited to participate in this long term follow-up study. After unblinding of the OTH/OZ1-INT-1 study, any patients in the placebo arm will be withdrawn from this protocol.

6. CONCOMITANT THERAPY AND ACTIVITIES

Information on current medications or other therapies will not be collected, unless required for submission of a Serious Adverse Event report.

7. STUDY EVALUATIONS

7.1 Study Procedures By Visit[†]

The Time and Events Schedule included in the Synopsis summarizes the frequency and timing of the various efficacy and safety measurements.

Visit schedules are fixed from the day of the original infusion of autologous CD34+ cells as per the OTH/OZ1-INT-1 protocol. Blood samples may be taken up to 1 week prior to the other assessments.

Table 3: Long term follow-up allowed visit intervals.

Visit interval	Allowed window
6 months	± 6 weeks
12 months*	± 12 weeks*

* Except the End-of-Study visit, which will be scheduled at a date no later than 30 November 2017.

In the event that a subject is unable to attend the clinic within the allowed visit window, a telephone interview can be conducted to collect information on important medical events since the last study visit (or telephone interview). Refer to [Appendix 2](#) for the interview questionnaire. If the clinical trial site is unable to contact the patient directly a nominated secondary contact will be contacted. A patient will be considered to be lost-to-follow-up, at any stage of the clinical trial, after three failed documented attempts (telephone calls, certified letters, e-mail requests) to contact either the patient or a nominated secondary contact. A lost or withdrawn patient may re-enter this long term follow-up protocol at any stage up until 30 November 2017.

2.5 to 5.0 years post-infusion[†]

Visits will be at six monthly intervals from year 2.5 to year 5.0 post-infusion.

The long term follow-up visits at Year 2.5, 3.5 and Year 4.5 post-infusion will have the following assessments:

- Clinical history and physical examination including a detailed record of:
 - exposure to possible mutagenic agents e.g. radiotherapy or chemotherapeutic agents
 - new malignancies
 - new or exacerbated preexisting neurologic, rheumatologic, autoimmune and hematologic disorders
- Complete Blood Count (CBC)/differential and platelet count.
- Testing for clonality of OZ1/LNL6 integration in PBMC samples (PCR) if the percentage of cells marked by the vector (quantitative OZ1 DNA-PCR) is greater than or equal to 1% of the test cell population.
- Analysis of quantitative marking of the gene transfer product (OZ1 and LNL6) in peripheral blood mononuclear cells (PBMC) will be performed as part of the testing of predominant integration sites. These marking data will also be analyzed independently of the integration analysis to detect changes in the number of cells carrying the gene transfer product.
- Recording of AEs.
- Contact details updated for subject and nominated secondary contact.

The long term follow-up visits at Year 3, 4 and 5 post-infusion will have the following assessments:

- Clinical history and physical examination including a detailed record of:

OZ1: Clinical Protocol OZ1-HV1-202 Amendment 4; 07 June 2017

- exposure to possible mutagenic agents e.g. radiotherapy or chemotherapeutic agents
- new malignancies
- new or exacerbated preexisting neurologic, rheumatologic, autoimmune and hematologic disorders
- Complete Blood Count (CBC), differential and platelet count.
- Archival storage of plasma and PBMC samples for safety testing including Replication-Competent Retrovirus (RCR) as required.
- Testing for clonality of OZ1/LNL6 integration in PBMC samples (PCR) if the percentage of cells marked by the vector (quantitative OZ1/LN6 DNA-PCR) is greater than or equal to 1% of the test cell population.
- Analysis of quantitative marking of the gene transfer product (OZ1 and LNL6) in peripheral blood mononuclear cells (PBMC) will be performed as part of the testing of predominant integration sites. These marking data will also be analyzed independently of the integration analysis to detect changes in the number of cells carrying the gene transfer product.
- Recording of AEs.
- Contact details updated for subject and nominated secondary contact.

Annual Visits Year 5+ post infusion and End-of-Study visit[†]

- Clinical History and Physical Examination including a detailed record of:
 - exposure to possible mutagenic agents e.g. radiotherapy or chemotherapeutic agents
 - new malignancies
 - new or exacerbated preexisting neurologic, rheumatologic, autoimmune and hematologic disorders
- Complete Blood Count (CBC), differential and platelet count.
- Archival storage of plasma and PBMC samples for safety testing including Replication-Competent Retrovirus (RCR) as required.
- Testing for clonality of OZ1/LNL6 integration in PBMC samples (PCR) if the percentage of cells marked by the vector (quantitative OZ1/LNL6 DNA-PCR) is greater than or equal to 1% of the test cell population.
- Analysis of quantitative marking of the gene transfer product (OZ1 and LNL6) in peripheral blood mononuclear cells (PBMC) will be performed as part of the testing of predominant integration sites. These marking data will also be

OZ1: Clinical Protocol OZ1-HV1-202 Amendment 4; 07 June 2017

analyzed independently of the integration analysis to detect changes in the number of cells carrying the gene transfer product.

- Recording of AEs.
- Contact details updated for subject and nominated secondary contact.

In the event that a recipient does not report for an in-person End-of-Study visit, a telephonic follow-up will be an acceptable alternative.

Unscheduled Assessments[†]

In addition to the annual follow up visit, unscheduled procedures may be performed in the event of an adverse event or as directed by the Investigator.

7.2 Safety Evaluations

The study will include the following evaluations of safety and tolerability:

- Adverse Events (AEs): AEs will be reported by the patient (or where appropriate by the patient's legally authorized representative) for the duration of the study. Further details on adverse event reporting are provided in Section 10.
- **Clinical Laboratory tests as follows:**

The following testing will be completed as designated in the Time & Events Schedule:

Gene Transfer Product Safety Testing

1. Testing for clonality of OZ1/LNL6 integration in PBMC using PCR.
 - Testing for clonality of OZ1/LNL6 integration in PBMC samples (PCR) will proceed if the percentage of cells marked by the vector (quantitative OZ1/LNL6 DNA-PCR) is greater than or equal to 1% of the test cell population.
 - If a predominant integration site is detected, the patient will be retested within three months to determine if it persists. If so, the site of integration of OZ1 will be sequenced and mapped to the human genome to determine any association with a known human oncogene. In all instances that a predominant integration site is present and, particularly when there is expansion of a cellular clone, the patient will be monitored closely for signs of cancer, so that any potential treatment can be initiated as early as possible.

OZ1: Clinical Protocol OZ1-HV1-202 Amendment 4; 07 June 2017

- “Predominant integration site” is defined as an integration site which has a density of at least 50% of the total signal detected by PCR, when the percentage of cells marked by the vector (quantitative OZ1/LNL6 DNA PCR) is >1% of the test cell population.
 - Any confirmed finding of a predominant integration site, i.e. present on at least two consecutive samples, will be reported as an SAE.
2. PBMC samples will be archived and will be tested for the presence of RCR using primers specific for amphotropic *env* retroviral gene sequences if required.
- PBMC cell pellets and cryopreserved cells will be archived for RCR testing. RCR testing by PCR will be completed on these samples only if there is a clinically relevant adverse event (e.g. neoplasm) or an RCR test during the OTH/OZ1-INT-1 study was positive.
 - Any samples found to be positive for amphotropic *env* sequences will be analyzed further by biological assay to confirm and identify any putative RCR.
 - Any confirmed positive finding of RCR will be reported as a SAE.
3. Archival plasma and PBMC samples will be collected annually for the duration of the long term follow-up protocol.

Hematology

This will include red blood cell count, hemoglobin, hematocrit and platelets, white blood cell count with differential (neutrophils, lymphocytes, monocytes, eosinophils and basophils).

An Investigator must interpret the laboratory reports. Any clinically significant changes that require an intervention (e.g. concomitant medication or other treatment or investigation) must be recorded in the source documents.

Autopsy

If a patient dies during the long-term follow up, an autopsy will be requested to determine the extent of gene transfer into bone marrow, spleen, lymph nodes and gonadal tissue, as well as any potentially transformed tissues (e.g. lymphomas, leukemia). A separate informed consent for autopsy will be requested. Patients may

sign the consent for autopsy at the time of enrollment. Autopsy will not be required for patients randomized to placebo (after unblinding of the OTH/OZ1-INT-1 trial).

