### **8.3. PREDOMINANT INTEGRATION SITE TEST**

Predominant integration site is defined as an integration site which has a density of at least 50% of the total signal detected by PCR, when the percentage of cells marked by the vector (quantitative OZ1/LNL6 DNA PCR) is greater than 1% of the test cell population. Results are recorded as part of the initial study information and at each follow-up visit.

A confirmed finding of a predominant integration site is a finding that is present on at least 2 consecutive samples. A predominant integration site finding will be reported as an SAE. Predominant integration site results will be listed only, no summary tables will be presented.

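### A predominant integration site found just above 1% marking cannot be confirmed on a retest that reads below 1%, even if the same site still dominates; the 1% threshold and the SAE condition are also each stated two ways

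*Protocol*

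**What the plan says.** Protocol 7.2 (Gene Transfer Product Safety Testing) sets out a chain of rules.

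- **Testing.** Clonality testing of PBMC samples goes ahead if marking "is greater than or equal to 1% of the test cell population". Footnote 2 of the Time and Events Schedule gives the complement: if marking "is less than 1% of the test cell population, the site of integration will not be investigated". SAP Tables 1 and 2 repeat that footnote.
- **Definition.** A predominant site must meet two conditions: one on its share of signal ("density of at least 50% of the total signal detected by PCR") and one on the level of marking in the sample ("when the percentage of cells marked by the vector (quantitative OZ1/LNL6 DNA PCR) is >1% of the test cell population"). SAP 8.3 uses the same above-1% definition.
- **Retest.** After a predominant finding, "the patient will be retested within three months to determine if it persists".
- **Mapping.** "If so, the site of integration of OZ1 will be sequenced and mapped to the human genome".
- **Confirmation and reporting.** "Any confirmed finding of a predominant integration site, i.e. present on at least two consecutive samples, will be reported as an SAE". Protocol 10.1 also lists only a confirmed finding as a special SAE. SAP 8.3 agrees on what confirmation means ("A confirmed finding of a predominant integration site is a finding that is present on at least 2 consecutive samples"), but its next sentence makes a predominant site finding an SAE without requiring confirmation.

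No passage sets a different marking rule for the retest sample, or says how to classify a retest that reads below 1%.

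**The concern.** Clonal expansion with a predominant insertion site is objective 1a in both documents. The retest exists to answer one question: is the same site still dominant? As written, it also asks whether total marking reads above 1% a second time. These are different questions. Near the threshold the second can fail through measurement variation alone.

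If it fails, the site assay is not run and persistence is unknown, but the rules let the result pass as non-confirmation. Mapping depends on persistence and the special SAE rule depends on confirmation, so neither is triggered by that retest. The documents also do not say whether an uninvestigated sample counts as one of the consecutive samples. If it does, it breaks the run, and a later positive has to start again.

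The two inequalities and the two SAE statements add a second problem: two teams could classify the same patient differently.

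**Working it through.** The plan states no figure for this rule, so there is nothing to reproduce. The check is a substitution of the rules into each other, followed by an illustration.

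**Step 1: substitute the definition into the confirmation rule.** Let m be the marking reading (%) and d the site's share of PCR signal (%).

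- Tested if m ≥ 1.
- Predominant if d ≥ 50 and m > 1.
- Confirmed if predominant on two consecutive samples, so d₁ ≥ 50, d₂ ≥ 50, m₁ > 1 **and** m₂ > 1.

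For a first sample that was predominant, and a retest in which the site still gives at least 50% of the signal:

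| Retest marking | Site assay run? | Can meet the definition? | Confirmed? |
|---|---|---|---|
| above 1% | yes | yes | yes |
| exactly 1% | yes | no | no |
| below 1% | no | no | no; classification not stated |

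For example, a first reading of 1.2% and a retest of 0.9% with the same dominant site cannot be confirmed on that retest.

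**Step 2: how often could this happen?** SAP 7.1 shows that marking is measured in triplicate. Neither document gives a CV or other measure of repeatability, so what follows is an assumption. Take the reading as log-normal with median equal to true marking M (%), log-scale SD s, independent errors on the two samples and no biological change. Then

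P(retest < 1%) = Φ(−ln M / s).

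| True marking M | ln M | s = 0.2 | s = 0.3 | s = 0.4 |
|---|---|---|---|---|
| 1.0% | 0 | 50% | 50% | 50% |
| 1.2% | 0.182 | 18% | 27% | 32% |
| 1.5% | 0.405 | 2% | 9% | 16% |
| 2.0% | 0.693 | 0% | 1% | 4% |

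For instance, at M = 1.2% and s = 0.2, 0.182/0.2 = 0.91 and Φ(−0.91) = 0.18.

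A wider range, using s = √ln(1 + CV²), gives the following:

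- CV 10%: 3% at M = 1.2% and under 0.1% at 1.5%.
- CV 50%: 35% at 1.2%, 20% at 1.5%, 7% at 2.0% and 1% at 3.0%.

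So the effect lies mainly between about 1% and 1.5%, reaching about 2% if the assay is imprecise.

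**Step 3: the two inequalities.** At-least-1% (testing) and above-1% (definition, SAP 8.3, title of SAP Listing 16.2.6) differ only for a reading recorded as exactly 1%. Such a sample is assayed but cannot be positive. How often that occurs depends on rounding, which is not stated.

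**Step 4: the SAE condition.** Protocol 7.2 and 10.1 require a confirmed finding. The SAE sentence in SAP 8.3 does not, and SAP 8.2 likewise names a predominant integration site as a serious condition without the word confirmed. The same unconfirmed finding is outside the special SAE rule in one document and inside it in the other.

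**The case against.** The strongest reply is that the retest threshold is inferred. The retest sentence has its own purpose and no marking condition, and mapping follows from persistence, not from the word confirmed. It is true that no sentence states a retest threshold outright. But footnote 2 puts the below-1% rule and the retest rule in the same note with no exception, and the definition carries the above-1% condition into every sample that counts towards confirmation.

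A reader might infer that mapping and SAE reporting would never happen for such a patient. The documents do not support that:

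- Integration testing recurs at each scheduled visit, and unscheduled procedures are allowed.
- Cancer monitoring applies whenever a predominant site is present, without confirmation.
- Under Protocol 10.1 the investigator may judge an event serious. Under 10.2 death, and malignancy other than basal or squamous cell carcinoma, are reportable whatever the cause.
- Read literally, SAP 8.3 would report even an unconfirmed finding.

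These safeguards stand, with limits. Visits are annual after year 5, the study closes by 30 November 2017, and an end-of-study contact by telephone yields no sample.

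A reader might also infer that a primary safety endpoint is biased. No primary endpoint is defined. SAP 8.3 lists these results without summary tables, and Listings 16.2.6 and 16.2.7 are planned to show site results and re-tests for all patients.

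Two further points stand. An expanding clone would, other things equal, raise marking away from the threshold. Amendment 4 is dated 07 June 2017, so few new samples could be affected. However, the final analysis expected in 2018 is cumulative, so how any retest below 1% is classified still matters.

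**Conclusion.** The point holds as a gap in the confirmation rule. A retest below 1% is not examined, so it cannot answer whether the site persists, yet the definition leaves it unable to confirm. This bears on objective 1a, and any error runs in one direction: a persisting site goes unconfirmed on that retest.

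The size is modest and local. Under the assumed log-SD of 0.2 to 0.4, the chance of a sub-1% retest with no biological change is 18–32% at true marking 1.2% and 0–4% at 2.0%. These figures illustrate the rule and are not estimates for this assay. Nothing in the documents shows how many patients, if any, lie near 1%.

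The mismatch between at-least-1% and above-1%, and that between the SAP and protocol SAE statements, are literal and need no assumption. The first is minor in effect. The second decides whether an unconfirmed finding is an SAE.

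**What to change.** In Protocol 7.2, Time and Events footnote 2 (with its copies in the SAP visit-schedule tables) and SAP 8.3:

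1. Make the confirmation step answer the persistence question. Analyse the retest sample for the same site where vector DNA can be amplified, and list its marking percentage beside the result. If it is not analysed, class it as not evaluable, not as unconfirmed.
2. Reconcile at-least-1% in the testing rule with above-1% in the definition, SAP 8.3 and the title of Listing 16.2.6. Which inequality to use is for the sponsor to settle.
3. Reconcile SAP 8.3's unconditional SAE sentence (and the matching entry in SAP 8.2) with the confirmed-finding rule in Protocol 7.2 and 10.1. Which condition applies is likewise for the sponsor.

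The cost is wording in both documents and at most one integration assay on a retest sample that is drawn anyway. The downside is that site profiles are less precise at low marking, so an occasional extra finding may need review. Listing the marking percentage beside the result lets a reader judge that.
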